12.4 Analysis of Secondary Objectives

Pharmacokinetic studies

Plasma samples will be analyzed via a validated high performance liquid chromatography/tandem mass spectrometry (HPLC/MS-MS) method for plasma selinexor concentration. Selinexor concentration data will be analyzed in a non-linear mixed effects population PK model with potential covariates including, but not limited to: age, body weight, gender, disease state, baseline hepatic or renal function, concomitant medications, and treatment. Details of the population PK analysis, including software, post-processing and statistical analysis, will be outlined in a separate Data Analysis Plan, to be completed prior to database lock. Interim analysis may be conducted on draft plasma selinexor concentration data throughout the study. Summary statistics, including mean, median, standard deviation, coefficient of variation and group size may be compiled and reported during the study. Interim analysis of key selinexor PK parameters and key biomarker analyses may be performed in order to provide a pharmacokinetic-pharmacodynamic assessment throughout the study.

Efficacy

The efficacy of the combination of selinexor, fludarabine, and cytarabine, as measured by the complete response (CR) rate and the overall response (OR) rate (CR + CRi + PR) will be assessed for the patients enrolled at the RP2D. The rates of CR and OR will be presented as a point estimate with a 95% exact binomial confidence interval.

The therapy offered in the phase II portion of this protocol will be considered worthy of further study if success, as defined in section 12.3, is achieved for 16 or more of the 39 patients. This design has a 10% probability of declaring the therapy worthy of further study under the null hypothesis that the true success rate is 30%. This design has a 90% probability of declaring the therapy worthy of further study under the alternative hypothesis that the true success rate is 50%. This design was obtained by the R command *ph2simon*(*pu* = 0.3, *pa* = 0.5, *ep1*=0.1, *ep2*=0.1) defined in version 1.0.11 of the R package *clinfun*. The method of Koyama and Chen as implemented in the *twostage inference* procedure of the *clinfun* R package will be used to compute the confidence interval for the success rate.²²

Responsible investigator: [name], PhD
Responsible statistician: [name]

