Appendix I: Selinexor Dose Rounding Chart

Appendix II: Performance Status Criteria

Appendix III: Tests Performed for Routine Care and for Research

Appendix IV: Selinexor Dose Modification Guidelines for AEs Associated with Selinexor

Appendix V: Specimen Submission Guidelines

1.0 OBJECTIVES

1.1 Primary Objective

- 1.1.1 To determine a tolerable combination of selinexor, fludarabine, and cytarabine in pediatric patients with relapsed or refractory hematologic malignancies including acute myeloid leukemia (AML), acute lymphoblastic leukemia (ALL), mixed phenotype acute leukemia (MPAL) and myelodysplastic syndrome (MDS) in the phase I portion of the study.
- 1.1.2 To estimate the overall response rate, as defined by complete response or complete response with incomplete count recovery, of selinexor in combination with fludarabine and cytarabine for patients with relapsed or refractory AML in the phase II portion of the study.

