12.0 STATISTICAL CONSIDERATIONS

The primary objective of the phase I portion of this study is to determine a tolerable combination of selinexor, fludarabine, and cytarabine in patients with relapsed or refractory hematologic malignancies including acute myeloid leukemia (AML), acute lymphoblastic leukemia (ALL), and myelodysplastic syndrome (MDS). Although disease response to treatment will be explored, this phase I portion of the study is not designed to yield a formal evaluation of the efficacy of this regimen.

The primary objective of the phase II portion of the study is to estimate the overall response rate, as defined by complete response or complete response with incomplete count recovery, of selinexor in combination with fludarabine and cytarabine for patients with relapsed or refractory AML. This will be assess be assessing the null hypothesis that overall response rate is $< 30\%$, as specifically described below.

Responsible investigator: [name], PhD
Responsible statistician: [name]

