12.3 Phase II Sample Size/Accrual Rate

For purposes of this Phase II evaluation, we define a success as complete remission, complete remission with incomplete count recovery, or, for patients who are enrolled with <5% blasts, the achievement of MRD negativity, by the end of one course of therapy. Patients who die before reaching this milestone will be counted as failures for purposes of this Phase II design. We will use Simon's minimax two-stage design for the Phase II component.²² In the first stage, we will enroll 28 patients. Patients who have been enrolled on the dose expansion cohort and who meet the eligibility criteria for the Phase II portion of the study, will be included in the analysis. The study will stop at any point it becomes impossible to obtain 8 or more successes (CR or CRi or MRD negativity) among the first 28 patients. If 8 or more successes are observed among the first 28 patients, the study will continue to enroll an additional 11 patients for a total of 39 patients. For the phase I portion of the trial, we enrolled 18 patients in 15 months, for an accrual rate of 1.2 patients/month. Conservatively assuming each of the four additional participating sites enroll one patient per year, the accrual will increase to 1.5 patients/month. At this rate the study will be open for as little at 19 months or up to as long as 26 months.

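### Phase II 'overall response rate' means CR+CRi in the primary objective but CR+CRi+PR in section 12.4, while the decision rule tests a differently defined 'success'

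*Combined protocol and SAP*

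**What the plan says.** Three places define the response measure for Phase II.

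- **Primary objective and statistical preamble.** Section 1.1.2 sets out "To estimate the overall response rate, as defined by complete response or complete response with incomplete count recovery". Section 12.0 repeats that definition and says the objective will be addressed by "assessing the null hypothesis that overall response rate is" below 30%.
- **Design section.** In 12.3, "we define a success as complete remission, complete remission with incomplete count recovery", and the definition continues with an MRD route: "for patients who are enrolled with <5% blasts, the achievement of MRD negativity, by the end of one course of therapy". The stage 1 rule (at least 8 of 28) counts these successes.
- **Efficacy analysis.** Section 12.4 states that "the overall response (OR) rate (CR + CRi + PR) will be assessed for the patients enrolled at the RP2D", and that "The rates of CR and OR will be presented as a point estimate with a 95% exact binomial confidence interval". The next paragraph applies the final rule (at least 16 of 39), the 30% and 50% hypotheses and a Koyama-Chen interval to success as defined in 12.3.

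Section 8.1.3 defines PR as 5% to 25% marrow blasts with at least a halving of the blast percentage. Sections 8.1.1 and 8.1.2 define CR and CRi by <5% blasts without extramedullary disease, separated by count recovery. Section 3.1.3 admits patients on rising MRD without requiring 5% blasts.

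**The concern.** One name, overall response rate, carries two definitions within the same plan, and nothing reconciles them. In 1.1.2 and 12.0 it is the Phase II primary measure and excludes PR. In 12.4 it includes PR. A report that follows 12.4 would give, under the primary endpoint's name, a rate that counts patients with up to 25% residual blasts as responders. Section 12 gives no separate analysis of a CR+CRi rate. The closest planned quantity is success, which has a different name and a special criterion for one group of entrants.

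At stake is the meaning of the reported result. A reader who takes the definition and the null from 12.0 may set the 12.4 figure against a 30% benchmark that was not chosen for it.

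**Working it through.** **Step 1. Reproduce the design.** Inputs: 28 patients in stage 1, continue at 8 or more (12.3); 39 in total, go at 16 or more, null rate 0.30, alternative 0.50, both error limits 0.1 (12.4). For a true rate p:

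P(go | p) = Σ over x = 8 to 28 of C(28, x) p^x (1−p)^(28−x) × P[Bin(11, p) ≥ 16 − x]

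- p = 0.30: 0.0943 (stated 10%).
- p = 0.50: 0.9001 (stated 90%).
- Probability of stopping at stage 1 when p = 0.30: P[Bin(28, 0.30) ≤ 7] = 0.365. Expected sample size 28 + (1 − 0.365) × 11 = 35.0.

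An exhaustive minimax search under the same limits returns the same design (28, 8, 39, 16). The 0.0943 lies below 0.10 because the binomial is discrete under a 0.10 ceiling. The design figures are sound.

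**Step 2. Classify the same patients under each definition.** Status after one course, no extramedullary disease:

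| Patient | 1.1.2 and 12.0 overall response (CR+CRi) | 12.3 success | 12.4 overall response (CR+CRi+PR) |
|---|---|---|---|
| Entered with ≥5% blasts, now <5% | yes | yes | yes |
| Entered with ≥5%, now 5–25% with at least a 50% fall | no | no | yes |
| Entered with <5%, still <5%, MRD negative | yes | yes | yes |
| Entered with <5%, still <5%, MRD positive | yes | no if the MRD clause replaces CR/CRi for this group; yes if it only adds a route | yes |

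The second row separates 12.4 from both other definitions. The fourth row can separate success from both overall response rates. Such a patient meets the marrow criterion for CR or CRi at baseline, so either overall response rate can count that patient as a responder without any treatment effect.

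**Step 3. See which analysis attaches to which definition.** The go rule, the numerical hypotheses and the two-stage interval attach to success. The single-stage exact interval attaches to the CR rate and to CR+CRi+PR. The 12.0 null attaches to CR+CRi. Success is judged by the end of one course; 12.4 gives no time limit for its overall response rate.

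**Step 4. Illustrate the size (assumptions only).** The documents give no PR rate for this regimen. Suppose the true CR+CRi rate is 30%, PR adds a fixed number of points, and someone wrongly applied the two cut-offs to CR+CRi+PR. The Step 1 formula at p = 0.30 plus the increment gives:

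| Assumed PR increment | Chance of clearing both cut-offs |
|---|---|
| 0 points | 0.094 |
| 5 points | 0.264 |
| 10 points | 0.508 |
| 15 points | 0.744 |
| 20 points | 0.900 |

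So the 30%/50% benchmarks have no valid meaning for a PR-inclusive rate. The only PR count in the documents is in Table 2, an adult phase I study of selinexor: CR+CRi is (5 + 1)/37 = 16.2%, and adding 2 PR gives 8/37 = 21.6%. That shows PRs occur; it does not estimate their rate with this paediatric combination.

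**The case against.** The strongest reply is that this is a labelling conflict and no more. Most of that reply stands.

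- **The decision is not in doubt.** A reader might infer that the go rule is ambiguous, or that the trial tests a PR-inclusive rate. The documents do not support this: 12.4 refers the rule to the 12.3 definition, states both hypotheses on the success rate and plans a two-stage interval for it. Nowhere does the plan compare CR+CRi+PR with 30%.
- **The tested rate is not missing.** A reader might infer that the primary quantity goes unestimated. For entrants with ≥5% blasts, success is exactly CR+CRi, and success has its own interval. Read literally as an extra route, the MRD clause adds almost nobody to CR+CRi; read as a substitute, it is stricter for entrants with <5% blasts only.
- **A reported response rate above 30% with a failed test is not caused by PR.** CR+CRi alone can do this: 12/39 = 30.8% up to 15/39 = 38.5% all exceed 30% and miss 16/39 = 41.0%. That follows from the cut-off and would remain after the fix.
- **The 12.4 components are visible.** They are spelled out under a heading for secondary objectives, so a separate secondary endpoint may be meant. But section 1.2 lists only a pharmacokinetic objective, and a secondary endpoint should not carry the primary endpoint's name with another definition.

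What the reply does not remove is the conflict between 1.1.2 and 12.0 on one side and 12.4 on the other, or the absence of the MRD criterion from the stated primary objective.

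**Conclusion.** The Phase II primary measure is defined inconsistently, and the text is wrong as written. The rate that 12.4 reports as overall response counts PR and leaves out the MRD criterion, so it is neither the rate in the primary objective nor the rate that is tested. This affects the labelling and interpretation of a reported result. It does not affect the sample size, the cut-offs, alpha (0.094), power (0.900) or the go decision.

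The numerical effect on the reported rate is unknown. It depends on how many patients have PR as their response and how many enter with <5% blasts, and the documents give neither for this regimen. The increments in the illustration are assumptions and should be labelled so wherever they are used.

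**What to change.** 1. In 1.1.2 and 12.0, make success as defined in 12.3 the Phase II primary endpoint. In 12.0, state the null as a success rate of 30% or less, in line with the hypotheses already in 12.4.
2. In 12.4, rename the PR-inclusive measure 'CR+CRi+PR rate', label it secondary and descriptive, and state that it is not compared with the 30%/50% benchmarks.
3. If a CR+CRi rate is also reported, state how patients enrolled with <5% blasts are classified, since they can meet the CR/CRi marrow criterion at baseline. Simply moving the name overall response to plain CR+CRi would leave two competing measures and this problem unsolved.

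The cost is a few sentences in 1.1.2, 12.0 and 12.4. Design, conduct and data collection do not change.

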3.0 ELIGIBILITY CRITERIA AND STUDY ENROLLMENT

3.1 Inclusion Criteria

According to institutional and NIH policy, the study will accession research participants regardless of gender and ethnic background. Institutional experience confirms broad representation in this regard.

- 3.1.1 **Phase I (completed)**: Participants must have a diagnosis of AML, MDS, ALL or MPAL and must have disease that has relapsed or is refractory to chemotherapy, or that has relapsed after hematopoietic stem cell transplantation (HSCT)
- a) Refractory disease is defined as persistent disease after at least two courses of induction chemotherapy.
 - b) Patients with AML, MPAL or MDS are eligible at first or subsequent relapse, whereas patients with ALL are eligible at second or subsequent relapse or any relapse that is refractory to salvage chemotherapy.
 - c) Patients with AML or ALL must have $\geq 5\%$ leukemic blasts in the bone marrow or increasing levels of MRD in the bone marrow as assessed by flow cytometry. If an adequate bone marrow sample cannot be obtained, patients may be enrolled if there is unequivocal evidence of leukemia in the peripheral blood.
- 3.1.2 **Phase II**: Participants must have a diagnosis of AML and must have disease that has relapsed or is refractory to chemotherapy, or that has relapsed after hematopoietic stem cell transplantation (HSCT)
- Refractory disease is defined as persistent disease after at least two courses of induction chemotherapy.
 - Patients are eligible at first or subsequent relapse or any relapse that is refractory to salvage chemotherapy.
- 3.1.3 Patients must have $\geq 5\%$ leukemic blasts in the bone marrow and/or increasing levels of MRD in the bone marrow as assessed by flow cytometry. If an adequate bone marrow sample cannot be obtained, patients may be enrolled if there is unequivocal evidence of leukemia in the peripheral blood.
- 3.1.4 Adequate organ function defined as the following:
- Direct bilirubin ≤ 1.5 x institutional upper limit of normal (IULN)
 - AST (SGOT)/ALT (SGPT) < 3 x IULN
 - Creatinine within normal institutional limits for age
- 3.1.5 Prothrombin time (PT) and partial thromboplastin (PTT) ≤ 1.5 x IULN.
- 3.1.6 Age criteria: Patients treated at collaborating sites and current St. Jude patients who are on therapy or within 3 years of completion of therapy must be ≤ 24 years old. All other St. Jude patients must be ≤ 21 years old.
- 3.1.7 Patients must be able to swallow tablets.

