4.0 TREATMENT PLAN

4.1 Overview

Patients must have fully recovered from the acute effects of all prior therapy before starting selinexor. In addition, at least 14 days must have elapsed since the completion of myelosuppressive therapy or gemtuzumab ozogamicin and the first dose of selinexor. At least 24 hours must have elapsed since the completion of low-dose or non-myelosuppressive therapy, such as hydroxyurea, vincristine, steroids, or low-dose cytarabine (up to 100 mg/m²/day), and the first dose of selinexor. For patients who have received prior HSCT, there can be no evidence of GVHD and greater than 60 days must have elapsed since the HSCT.

This study will include two phases. The dose-escalation phase will characterize the dose-limiting toxicities (DLTs) and determine the maximum tolerated dose (MTD) and recommended phase 2 dose (RP2D) of selinexor when given in combination with fludarabine and cytarabine. The RP2D will be chosen based on the MTD and totality of the data (clinical, PK, and PD data from this and other trials). The phase II cohort will further assess the safety and will explore the efficacy of this combination.

Selinexor will be given orally on days 1, 3, 8, 10, 22 and 24 of each cycle.

Fludarabine (30 mg/m²/dose IV over 30 minutes daily) and **cytarabine** (2 gram/m²/dose IV over 4 hours daily) will be given on days 16 (\pm 2 days) through 20 (\pm 2 days). Chemotherapy may be delayed if clinically indicated.

For patients who achieve CR or CRi with negative MRD or with MRD that has decreased at Day 15, the treating physician may continue single agent selinexor without fludarabine and cytarabine. In this case, selinexor should be given on days 1, 3, 8, 10, 15, 17, 22 and 24.

Patients who achieve CR or CRi status (as defined in Section 8.1) at day 15 (regardless of MRD status) may proceed directly to HSCT at the discretion of the treating physician.

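### The Section 12.4 overall response rate counts patients enrolled with <5% marrow blasts as responders if their blasts merely stay <5%, whatever their MRD does

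*Combined protocol and SAP*

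**What the plan says.** **Entry.** Section 3.1.3 requires at least 5% "leukemic blasts in the bone marrow and/or increasing levels of MRD in the bone marrow as assessed by flow cytometry". The and/or means that rising MRD is enough on its own.

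**Response categories.** CR (8.1.1) and CRi (8.1.2) share two conditions: marrow blasts below 5% confirmed by flow cytometry, and no extramedullary disease. Neutrophil and platelet counts decide which of the two applies. Only PR (8.1.3) requires a fall from baseline. MRD is not part of these categories, and Section 4.1 treats it as a separate matter: "CR or CRi status (as defined in Section 8.1) at day 15 (regardless of MRD status".

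**Phase II success.** Section 12.3 counts CR, CRi or, "for patients who are enrolled with <5% blasts, the achievement of MRD negativity, by the end of one course of therapy". The stage 1 rule lists the routes as "8 or more successes (CR or CRi or MRD negativity) among the first 28 patients". Section 12.4 then says that the therapy "will be considered worthy of further study if success, as defined in section 12.3, is achieved for 16 or more of the 39 patients".

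**Reported efficacy rates.** Section 12.4 also plans CR and OR rates with exact 95% binomial confidence intervals: "the overall response (OR) rate (CR + CRi + PR) will be assessed for the patients enrolled at the RP2D". This sentence has no MRD clause and no exception for patients enrolled below 5%.

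**Objective.** Section 1.1.2 reads "To estimate the overall response rate, as defined by complete response or complete response with incomplete count recovery", also without an MRD route.

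**The concern.** A response rate should count patients whose disease changed on treatment. A patient enrolled on rising MRD with, say, 2% blasts and no extramedullary disease is already in CR or CRi by Section 8.1. If the marrow is still at 2% after Cycle 1, the category is unchanged and the patient enters the Section 12.4 numerator, even if MRD has risen. Section 12.3 shows that the authors expected such patients and wanted a different yardstick for them. That yardstick was not carried into the Section 12.4 rates or into objective 1.1.2.

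At stake are the reported CR and OR rates of a single-arm trial, which readers will compare with response rates from other studies. A lesser issue is that Section 12.3 does not say that CR and CRi stop counting for these patients, so two analysts could classify the same patient differently.

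**Working it through.** **1. Does a <5% entrant meet CR or CRi at entry?** The conditions, one by one:

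| Condition in 8.1.1 / 8.1.2 | Patient enrolled with <5% blasts, no extramedullary disease |
|---|---|
| Blasts <5% by flow cytometry | Met at entry |
| No extramedullary disease | Met at entry |
| Blood counts | High enough gives CR; otherwise CRi. One of the two always applies |
| Baseline of at least 5%, or a decrease | Not required |
| MRD result | Not required |

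So the patient is CR or CRi at entry, and still is at the end of Cycle 1 if blasts stay below 5% and no extramedullary disease appears. A rise to 5% or more, or new extramedullary disease, leads to NR. The OR rate counts the stable patient for certain. The CR rate does so only if the counts also reach the 8.1.1 levels.

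**2. Effect on the Section 12.4 OR rate.** Let m be the number enrolled with <5% blasts who stay <5% without extramedullary disease, and r the response rate in the other patients. Neither is given for Phase II. I assume m = 1, 2 or 4, r = 30% or 50% (the null and alternative rates in Section 12.4), a denominator of 39, and that all <5% entrants stay <5%.

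- OR rate as written: [r(39 − m) + m]/39 = r + m(1 − r)/39
- OR rate among patients enrolled with at least 5% blasts: r
- Inflation: m(1 − r)/39

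| m | r = 30% | r = 50% |
|---|---|---|
| 1 | 0.7/39 = 1.8 points | 0.5/39 = 1.3 points |
| 2 | 1.4/39 = 3.6 points | 1.0/39 = 2.6 points |
| 4 | 2.8/39 = 7.2 points | 2.0/39 = 5.1 points |

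If k such patients are enrolled and only m of them stay <5%, the difference is (m − rk)/39, which is smaller.

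**3. The plan's own design figures.** The chance of declaring the therapy worthy is the sum, over x from 8 to 28, of P(Bin(28, p) = x) × P(Bin(11, p) ≥ 16 − x). This gives 0.0943 at p = 0.30 and 0.9001 at p = 0.50. The stated 10% and 90% are reproduced.

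**4. The same decision if CR/CRi also counted as success for <5% entrants.** Place m automatic successes at random among the 39 patients (hypergeometric split between the first 28 and the last 11) and give the others a 30% chance.

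| m | Chance of declaring worthy |
|---|---|
| 0 | 9.4% |
| 1 | 13.7% |
| 2 | 19.3% |
| 4 | 34.8% |

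These figures apply only on that reading of Section 12.3, which is not the natural one.

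**The case against.** The strongest reply is that the decision is already protected. Section 12.3 gives <5% entrants their own endpoint. If CR/CRi also counted for them, the MRD clause would add almost nothing: it would matter mainly for a patient kept out of CR/CRi by extramedullary disease. A reading that empties a purpose-written clause is unlikely to be intended. This stands. A reader might infer from the table in step 4 that the trial's 10% error rate is broken. The documents do not support that. The table describes a different endpoint, on which the expected success rate with m = 4 is already (4 + 0.3 × 35)/39 = 37.2%. What remains for Section 12.3 is an ambiguity: both lists of routes are joined by an or, and neither says which routes are closed to whom.

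Second, the Section 12.4 rates carry no hypothesis or threshold, and the success rate has its own interval by the Koyama and Chen method. That limits the consequence, but these are still planned efficacy results, and they are biased upward as written.

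Third, the CR rate is not automatic, because CR needs recovered counts after a myelosuppressive course. This stands, so the firm claim is about OR.

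Fourth, m is unknown and could be zero. This is true, although the special clause in Section 12.3 shows that such patients are expected.

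Two further inferences should be resisted. Section 12.0 gives the short definition of response but sends the reader to the specifics that follow, so it does not contradict Section 12.3. Section 4.7 uses the same categories for access to a second course, but it is permissive. An MRD restriction there would be a treatment decision, which a labelling problem does not justify.

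**Conclusion.** The concern holds for Section 12.4. As written, the OR rate counts as a responder any patient enrolled with <5% blasts and no extramedullary disease who simply stays that way, and the CR rate does so when blood counts qualify. The inflation of OR is m(1 − r)/39: between 1.3 and 7.2 points for the assumed m of 1 to 4 and r of 30% to 50%, and zero if no such patient is enrolled.

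The 16-of-39 decision is probably unaffected, because MRD negativity is the natural endpoint for these patients under Section 12.3. The wording there should still be closed. This should be corrected before analysis, but it is not a flaw in the design: the sample size, boundaries and stated error rates reproduce.

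**What to change.** - **Section 12.4:** report the CR and OR rates among patients enrolled with at least 5% blasts. Report the MRD-negativity rate separately for patients enrolled with <5% blasts. Show both denominators.
- **Section 12.3:** add that for patients enrolled with <5% blasts, MRD negativity is the only route to success and CR/CRi by Section 8.1 does not count.
- **Section 1.1.2:** refer to Section 12.3 for the definition of success.

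No new samples are needed. MRD is required before treatment (Section 6.1) and at Day 15 and all later time points (Appendix V). The sample size and the 8-of-28 and 16-of-39 boundaries stay.

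The cost is a smaller Section 12.4 denominator and slightly wider intervals. For example, suppose four patients are enrolled with <5% blasts and stay so, and 12 of the other 35 respond. The rate as written is 16/39 = 41.0% (exact 95% CI 25.6 to 57.9, 32.3 points wide). The proposed rate is 12/35 = 34.3% (19.1 to 52.2, 33.1 points wide).
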